The most frequent oral complications that have been reported in pediatric patients under chemotherapy are oropharyngeal mucositis (OM), xerostomia, caries and gingivitis, followed by opportunistic infections, which occur in up to 30% of cases; being more frequent those of fungal origin, although they can also be of bacterial or viral origin (candidiasis, cold sores, aphthous stomatitis and angular cheilitis). In the Mexican population, study by Castellanos et al., On oral lesions in children with acute lymphoblastic leukemia of the National Institute of Pediatrics, found that during the first 8 weeks of onset of chemotherapy, 71% of children developed some oral lesion the most frequent being OM (65%); which in severe grades (III or IV) was associated with neutropenia and malnutrition.⁶

Oral Mucositis

Oropharyngeal mucositis (OM) is a lesion of the oral and oropharyngeal mucosa that appears as a result of inflammatory changes in epithelial and subepithelial cells caused by the cytotoxic effects of chemo or radiotherapy.¹¹

The OM consists of four phases: 1) initial inflammation, 2) vascular and epithelial rupture 3) ulcerative / bacteriological and 4) healing. (7) It begins 3 to 10 days after the start of chemotherapy and may persist for 3 weeks. It reaches its maximum peak around 7 to 14 days and subsequently resolves slowly unless it is complicated by an infection; while, better resolution has been associated with neutrophil recovery.¹²⁻¹⁴

OM occurs at any age; however, it has been observed that the prevalence is higher in pediatric patients than in adults, which can be explained by the higher rate of cellular replication during childhood. It is estimated that 52 to 80% of children undergoing chemotherapy will experience some degree of OM, which varies according to the type of cancer and antineoplastic treatment. In general, children with hematologic malignancies present more frequently with OM than those with solid tumors.¹⁴

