Neurotoxicity: Zinc concentrations in the human brain remain in a range of less than 600-800 ng / L. The optimal concentration of free zinc in its ionic form in the cells is around 10 ng / L and when it drops to levels less than 0.06ng / L, apoptosis can be activated; while when levels exceed 60ng / L toxicity can be reached.²⁹The symptom that has been reported most frequently is headache.¹⁸

Hematotoxicity: Excessive ingestion of zinc sulfate chronically can induce anemia and leukopenia.¹⁹

Endocrines: Decreased HDL has been reported in men, while alterations in triglycerides have not been reported.²²

Immune: In a study with 11 volunteers it was observed that excess zinc (300 mg per day for 6 weeks) was associated with immunodeficiency and inflammatory response.²³

Toxicity management

Gastric lavage should be avoided, the administration of chelators such as milk, sodium and calcium at a dose of 50 to 75mg / kg / day is recommended.²²

The researchers' response to adverse reactions, allergic reactions and accidental intake are described in the investigator's manual.

Zinc and oral mucositis

The effectiveness of zinc for the prevention of OM was initially studied in patients with head and neck cancer receiving radiotherapy. Ertekin et al.²⁷ established the dose of 150 mg of zinc sulfate daily in adult patients, finding a reduction in the severity of OM. Lin et al.³⁰ administered zinc chelate at a dose of 75 to 100 mg/day in adults with oral and nasopharyngeal cancer, finding a reduction in the development of OM in patients with oral cancer.

Other studies have used zinc sulfate mouthwashes in adults with head and neck cancer in radiotherapy and in patients with acute myeloid leukemia in the hematopoietic progenitor cell transplant protocol, finding that there were no differences between the zinc group and the control group.^{31, 32} Other studies used L-carnosine zinc mouthwashes in adults with head and neck cancer receiving chemo / radiotherapy and in patients with leukemia in the transplant protocol, obtaining a reduction in the severity of the OM.^{33, 34}

To date, only 3 studies have been conducted in patients receiving chemotherapy, (11) one of them was conducted in patients with head and neck cancer; another in patients with myeloid leukemia and the last in patients with myeloid and lymphoid leukemia; being all in adults, who received 150 mg of zinc sulfate daily, resulting in a reduction in the severity of the OM.^{12, 37, 38} (See Table 3).

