Gholizadeh et al. ⁽³⁸⁾ (2017)	Chemotherapy	220 mg capsules equivalent to 50 mg of zinc sulfate 3 times / day 150 mg / day VS. Placebo	Myeloid and lymphoid leukemia 18 - 71 years old	Randomized clinical trial n = 140 4 weeks follow-up (week 2 and 4)	Reduction of severity of OM grade 3-4 p = 0.004
Rambod et al. ⁽¹²⁾ (2018)	Chemotherapy	220 mg capsules equivalent to 50 mg of zinc sulfate 3 times / day 150 mg / day VS. Placebo	Myeloid and lymphoid leukemia > 18 years	Randomized triple blind clinical trial n = 86 14 days WHO oral mucositis scale Oral Mucositis Index	OM prevention p = 0.01 OM severity reduction p = 0.01

OM; Oral Mucositis, HDC: High doses of chemotherapy, HPCT: hematopoietic progenitor cell transplantation.

There are currently no studies evaluating the effectiveness of zinc for the prevention of OM in pediatric patients receiving chemotherapy, so the purpose of this study is to conduct a clinical trial that evaluated the impact of the use of zinc for the prevention of OM in children with LAL in chemotherapy.

PROBLEM STATEMENT

The development of OM in patients with acute leukemia varies between 81.3% and 90% .8 The available literature recognizes the importance of prevention and treatment of OM, since it has an impact on the quality of life and even on the prognosis of disease in patients under chemotherapy. The better understanding of the pathophysiology of this entity has allowed the development of new therapies, among which the use of zinc, which has shown beneficial effects in the prevention of OM in adult patients with leukemia, and because they are not counted with studies in pediatric patients with ALL; The following research question arises:

What is the impact of the use of zinc for the prevention, incidence and reduction of the severity of oropharyngeal mucositis in patients with acute lymphoblastic leukemia in chemotherapy during the period from 2019 to 2020?

JUSTIFICATION

In the National Institute of Pediatrics, about 100 new cases of ALL enter each year, which will require a multidisciplinary approach throughout the course of cancer treatment, which includes the participation of the stomatologist, who must continually establish preventive and therapeutic measures of complications buccal, among which the OM stands out as a reason for frequent consultation.

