Cancer patients will experience pain, limitation and psychological involvement due to oral OM; this debilitating condition also significantly affects nutritional intake, oral care and quality of life, representing up to 21.9% of the reasons for hospitalization.8 OM, if not properly treated or associated with prolonged neutropenia, may end in septic shock and even the death of the patient.

The use of zinc has been studied as a low-cost alternative for OM, so the realization of this study will determine the effectiveness of the use of zinc for the prevention and reduction of complications due to OM in pediatric patients with ALL of the Institute National Pediatrics.

OBJECTIVE

To assess the impact of the use of zinc in the prevention, incidence and severity of oropharyngeal mucositis in patients with acute lymphoblastic leukemia in chemotherapy (induction and consolidation phase) of the National Institute of Pediatrics and the Children's Hospital of Mexico during the period from 2019 to 2020.

SPECIFIC OBJECTIVES

1. Determine the incidence of OM in patients with ALL assigned control group (Group 1: oral care + placebo) versus the intervention group (Group 2: oral care + zinc).
2. Identify if there are differences in OM severity between Group 1 and Group 2.
3. Identify if there are differences in the recovery time of the OM between Group 1 and Group 2.
4. Identify if there is an association between the severity of OM and severe neutropenia in both groups.

HYPOTHESIS

The use of zinc reduces the incidence and severity of OM in pediatric patients with ALL in chemotherapy compared to the control group.

MATERIAL AND METHODS

Type of study: Randomized, double blind clinical trial.

Duration of the intervention: Induction and consolidation phase of chemotherapy (2 to 2.5 months).

Inclusion Period: from August 2019 to May 2020.

Study population

Target population: patients of both sexes from 3 to 18 years of age with newly diagnosed or relapsed ALL during the period from 2019 to 2020.

Study population: patients of both sexes from 3 to 18 years of age with recently diagnosed or relapsed ALL treated by the Pediatric Oncology service of the National Institute of Pediatrics and the Children's Hospital of Mexico during the period from 2019 to 2020.

Selection criteria

Inclusion criteria: Patients aged 3 to 18 years with a recent diagnosis of ALL or relapse who accept by informed consent to participate in the study.

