Six randomized patients with a recent diagnosis of childhood cancer who start chemotherapy will be selected, data from the clinical record will be obtained to determine if it meets the inclusion criteria. The patient identified as eligible will be visited at his place of hospitalization or in the outpatient office of the Oncology Service.

The intervention will be assigned under the balanced block scheme. Children will be randomly assigned to each of the two treatment groups using sealed envelopes.

The sequence of procedures and the complete description of the instruments can be found in the Annex "Pilot test applicator manual".

[figure not shown]
Information collection method

A data record sheet will be filled out that includes the patient's identification form (name, age, sex), type of ALL, chemotherapy phase and blood count; which will be obtained from the clinical file. It will also include the table for the determination of the WHO OM scale, the oral hygiene index and the opportunistic infection registry.

Registration and processing method.

[figure not shown]
The data will be recorded in an Epidata database and analyzed using the STATA 14 statistical program.

FLOWCHART 1

In the previous study by Rambod et al. (12), a difference in the incidence of OM of 28% was obtained and from this, for the present study the estimated sample size was 106 subjects.

Complying with one of the principles that govern clinical trials, which is to reduce the risk of the operated subjects to the minimum possible, in case of observing adverse reactions the suspension of the study will be indicated; while if there are no complications, recruitment will continue until a sample size of 53 subjects is met and at this point the intermediate analysis will be performed as shown in Flowchart 2.

ETHICAL CONSIDERATIONS

In accordance with the principles and guidelines established by good clinical practices (BPC), in accordance with the principles set forth in the Helsinki Declaration of 1964 and with the support provided in the General Health Law, in the Regulations of the General Health Law in the area of provision of Health Care Services, which establishes that the individual welfare of the subjects must sometimes prevail in a study, over the interests of science and the community.

This study will be carried out with the strict observation of the recognized scientific principles and respect, handling the affected data anonymously and confidentially.

Consent

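### The 106 children and the stated power of 0.90 rest on 75% v 47% from an adult trial listed with 14 days of follow-up, while this trial counts mucositis in children over 2 to 2.5 months, and nothing bridges the two

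*Combined protocol and SAP*

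**What the plan says.** The Sample size calculation takes a control incidence of 75% and a zinc incidence of 47% from one cited zinc sulfate trial. It states alpha 0.05 and power 0.90, and arrives at 46 per group, or 53 after 15% losses. The text after Flowchart 1 repeats the basis: "a difference in the incidence of OM of 28% was obtained and from this, for the present study the estimated sample size was 106".

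Table 2 describes the source trial's population as "Myeloid and lymphoid leukemia > 18 years" and its design as "Randomized triple blind clinical trial n = 86 14 days WHO oral mucositis scale". Under Zinc and oral mucositis, the three chemotherapy studies, this one among them, are described as "being all in adults, who received 150 mg of zinc sulfate daily".

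This trial enrols "Patients aged 3 to 18 years with a recent diagnosis of ALL or relapse". Material and methods gives "Duration of the intervention: Induction and consolidation phase of chemotherapy (2 to 2.5 months", and Stages of the study schedules reviews on days 1, 4, 7, 14 and 21 of every cycle in both phases. The main Objective ties incidence to induction and consolidation. Specific objective 1 and the sample-size text name no window.

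The background holds other control rates:
- For children with ALL at the National Institute of Pediatrics, one of the two recruiting centres: "during the first 8 weeks of onset of chemotherapy, 71% of children developed some oral lesion the most frequent being OM (65" per cent).
- The section Oral Mucositis gives 52-80% for children on chemotherapy.
- The Problem Statement says: "The development of OM in patients with acute leukemia varies between 81.3% and 90" per cent.

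The sizing uses none of these.

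**The concern.** Cumulative incidence depends on how long patients are observed and on who they are. A rate seen in adults over 14 days is not automatically the planning rate for children observed for 60 to 75 days. The daily zinc amount also differs between the two trials (150 mg against 50-100 mg). I take no view on dose, but it is one more reason why a 28-point effect need not transfer.

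Incidence is specific objective 1 and the quantity that fixed the sample size. Two things are at stake. A null result would be read against a power that was worked out for another window and population. And because the sizing names no window, day 14, one cycle or the whole course could each later be called the incidence of OM.

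**Working it through.** **The plan's own figure.** With the numbers as substituted in the Sample size calculation:

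[1.96·√(2·0.75·0.25) + 0.84·√(0.75·0.25 + 2·0.47·0.53)]² / 0.28² = 45.84, so 46. Then 46 × 1.15 = 52.9, so 53 per group and 106 in all.

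The sample size reproduces. The power does not: a Z-beta of 0.84 corresponds to 80%, not 90%. That is a separate error. What follows would remain after it is corrected.

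**Assumptions.** 53 × 0.85 = 45.05, so 45 evaluable per group. Two-sided 0.05, uncorrected chi-square (the SAP names chi-square), power by exact binomial enumeration, no allowance for the interim look.

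**Carrying the effect over.** The documents give no paediatric zinc-arm rate, so I applied the source effect to each control rate p on four scales:
- relative risk 0.47/0.75 = 0.627; zinc rate 0.627·p
- hazard ratio ln(0.53)/ln(0.25) = 0.458; zinc rate 1 − (1 − p)^0.458
- absolute difference; zinc rate p − 0.28
- odds ratio (0.47/0.53)/(0.75/0.25) = 0.296; zinc odds 0.296·p/(1 − p)

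Example at p = 0.65: 0.627 × 0.65 = 0.407; 1 − 0.35^0.458 = 0.382; 0.65 − 0.28 = 0.37; odds 1.857 × 0.296 = 0.549, so 0.549/1.549 = 0.354.

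**Power with 45 per group** (zinc rate in brackets):

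| Control rate | Same relative risk | Same hazard ratio | Same 28 points | Same odds ratio |
|---|---|---|---|---|
| 65% (institute, 8 weeks) | 63% (41%) | 72% (38%) | 76% (37%) | 80% (35%) |
| 75% (as planned) | 79% (47%) | 79% (47%) | 79% (47%) | 79% (47%) |
| 81.3% (Problem Statement, lower) | 88% (51%) | 82% (54%) | 83% (53%) | 75% (56%) |
| 90% (Problem Statement, upper) | 97% (56%) | 84% (65%) | 91% (62%) | 59% (73%) |

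The 65% could also be read as a share of the 71% with lesions: 0.65 × 0.71 = 0.46 of all children. Power then runs from about 39% (same relative risk, 46% v 29%) to 84% (same 28 points, 46% v 18%).

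**Where 90% is reached.** At 65% control no scale gives 90%; even with all 53 per group evaluable the range is 70-86%. With the same relative risk, power is 90.3% at 83% control. With the same 28 points it takes about 90% control.

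**The case against.** Borrowing rates from the nearest leukaemia trial is ordinary planning, and the protocol says that no paediatric zinc study exists. The 75% is not out of line with the protocol's own figures: it lies inside 52-80%, and between 65% and 81.3-90%. Every zinc-arm rate above is an assumption. The 65% is itself ambiguous. That 75% and 47% are 14-day rates is read from the Table 2 entry; the text never labels them so. Much of the gap to 0.90 comes from Z-beta, since 75% v 47% already gives only 79%.

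All of this stands, and it limits the point to a missing justification and an unsupported single power figure. It does not supply the bridge. The institute's rate matches the disease, one of the centres and nearly the window, and the plan neither uses it nor says why not.

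A reader might go further and let the two-week rates recur at a constant rate, so that nearly every child has OM and the contrast vanishes. The documents contradict this: the assumption predicts 1 − 0.25^(56/14) = 99.6% control incidence at 8 weeks, against the 65% reported. An 8-week rate below the borrowed 75% also shows that window length alone does not settle the planning rate.

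**Conclusion.** The point holds as a mismatch. The sample size and the stated 0.90 come from a trial listed as adult with 14 days of follow-up, and the plan does not justify their use for children over induction and consolidation. At the best-matched control rate, 65%, power is 63-80%. Over 65%, 75%, 81.3% and 90% control together it runs from 59% to 97%, and down to about 39% if the 65% means 46% of all children.

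A reader might infer that the trial is underpowered for this reason. The documents do not support that: the error could go either way, because power rises above the 79% reference under several carry-overs at 81.3% and 90% control. What they do support is that no single power, and in particular not 0.90, can be quoted for this endpoint. The figures rest on 45 evaluable per group, two-sided 0.05, and the Table 2 entry being the follow-up behind 75% and 47%.

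**What to change.** In the Sample size calculation and in the text after Flowchart 1:

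1. State that the sized incidence of OM is cumulative over induction and consolidation.
2. Replace the single power of 0.90 by the power of 106 children (45 evaluable per group, two-sided 0.05) at control rates of 65%, 75%, 81.3% and 90%, naming the scale on which the effect is carried over, as tabulated above.
3. Say whether the institute's 65% is a share of all children or of those with lesions. If the latter, report the 46% case.
4. Say in one sentence why 75% v 47% was taken as the starting point, and that it comes from adults listed with 14 days of follow-up.

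Correct Z-beta as well, as a separate change. I would not rescue 75% v 47% by moving the sized endpoint to day 14 of the first cycle. That would fit the endpoint to a borrowed number and demote consolidation, where the background places high-dose methotrexate, a drug it links to OM.

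The cost is protocol wording and a wider, less favourable stated power. No patients or visits are added.

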Descriptive statistics will be used to characterize the population using measures of central tendency and dispersion for continuous variables and distributions of relative and absolute frequencies for categorical variables. Independent t-test and Chi-square test for the difference between the two study groups. Analysis of variance (ANOVA) to compare the two groups with respect to the OM in the five time periods.

METHODOLOGY

Randomization

The randomization will be taught by [name] [name], assigned to the Oncology service, who is unaware of the objective of the study.

The randomization technique will be carried out through sealed envelopes, which will indicate the bottle that will correspond to the patient, identified as treatment "A" and "B". Likewise, to ensure that the groups are balanced, blocks of 6 sealed envelopes containing 3 patients will be made for each group.

Blinding

The patient and the investigator will be blinded; for this, the 50 mg zinc and placebo tablets will be similar in size, color, shape, weight and taste; the bottles will be classified into codes A and B, which in turn will have the same shape, size and color. All of the above will be done through the Pharmaceuticals GREMAR S.A. de C.V., which is a Mexican company that has a line of food supplements located in Mexico City.

An independent investigator (who will be blinded for the purpose of the study) will be requested to receive the medications (zinc / placebo) prepared by the Pharmaceuticals GREMAR S.A. of C.V., so that it provides to the principal investigator only the bottles coded as "A" and "B". At the end of the intervention, the independent investigator will be asked to reveal the coding of the medications to determine which group (Group 1 placebo or Group 2 zinc) corresponds to treatment A and B respectively.

Instruments

WHO OM scale

The oral mucositis scale proposed by the World Health Organization (WHO) in 1979 will be used. This instrument was designed based on objective signs (erythema or ulcer) and subjective signs (mucosal sensitivity, ability to swallow).

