The classification includes 5 degrees as follows: grade 0, no changes in the oral cavity are detected; grade I, pain and erythema in mucosa, gums, tongue or palate; grade II, erythema and ulcers, still with a solid diet tolerance; grade III, oral ulcers, tolerance to pasty foods and liquid diets; and grade IV, ulcers, erythema, pain, inability to swallow fluids, impossible oral feeding, and narcotic requirement to relieve pain. The total score of this scale ranges from 0 to 4.

Visual scale of facial expressions

This scale was developed by Bieri in 1990 for use in children from 3 years. It is made up of faces with different expressions that represent a person who is happy because they do not feel pain, and it changes to a sad expression as the pain increases. Each face is assigned a score, to answer it, the patient is asked to select the face that best describes how he feels.

Standardization

It will be carried out through a series of clinical cases with clinical photographs of different degrees of OM, evaluated using the WHO's OM scale and contrasting the answers with an expert researcher in OM ([name] [name]).

The master's student and a social service student will be standardized, the evaluation will be in pairs and independently.

The weighted Kappa coefficient (k_p) for the degrees of OM will be calculated, until a minimum of 0.61 to 0.80 is obtained.

Stages of the study and data collection

The recruitment of patients will be carried out in the Oncology service of the National Institute of Pediatrics and the Children's Hospital of Mexico. Every day you will wonder if a new patient arrived with suspected leukemia or relapse. We will be aware of the result of the bone marrow aspirate confirming the diagnosis of ALL or relapse.

The master's student will present indicating that the reason for their vision is to inform them about the importance of oral health with respect to their current medical treatment and will give them information about the oral care that they should perform for the prevention of oral complications secondary to their disease and / or the drugs they will receive during their treatment. Visual material will be displayed by means of a computer / tablet device that includes information on oral care indicating brushing technique and making mouthwashes with bicarbonate solution. Likewise, it will explain what consists of

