oropharyngeal mucositis, how it relates to chemotherapy and the preventive measures they can perform. Finally, the complications that may occur during the OM will be explained, such as: difficulty in eating, speaking or swallowing, as well as the measures that must be taken to allow adequate recovery.

Parents will be invited to participate in the protocol explaining the objectives of the study, as well as its risks and benefits. In case of accepting to participate, informed consent and assent (in children over 12 years old) will be presented in accordance with the characteristics that are written in it.

The intervention will be assigned under the balanced block scheme. Children will be randomly assigned to each of the two treatment groups using sealed envelopes.

Oral examination, staining of dentobacterial plaque will be performed (the characteristics of the plaque revealing solution are described in the researcher's manual) for the determination of the oral hygiene index and explanation of brushing technique on day 0 of chemotherapy.

Patients who require dental caries treatment will be rehabilitated by the stomatology service according to their stomatological diagnosis and their general condition. A closed bottle containing 100 tablets (treatment A or B) will be provided according to the random assignment. It will be indicated to administer 1 or 2 tablets daily (according to the age of the patient) from day 1 of chemotherapy.

A written reminder will be provided to parents in which they must check each day if the tablet was taken.

Calls will be made every 3 days to verify that oral hygiene and tablet administration are being carried out; In addition, the reminder will be reviewed twice a week and the remaining tablets will be counted in the bottles.

During the course of chemotherapy (induction and consolidation phase) reviews will be performed on days 1, 4, 7, 14 and 21 of each cycle.

Maneuver

Group 1 (oral care + placebo): gentle tooth brushing with a soft bristle brush 3 times a day and mouthwash with baking soda after each meal (1/4 tablespoon of baking soda dissolved in water to make a mouthwash for 3 minutes) plus the consumption of 1 or 2 oral placebo tablets (mannitol) from day 1 of chemotherapy.

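### Two-letter bottle coding lets one tablet, or one by-letter table at the planned look at 53 subjects, expose every child's allocation; the SAP omits the look and no readable text keeps its result from the mucositis graders

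*Combined protocol and SAP*

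**What the plan says.** - **Coding.** Under Methodology, Blinding, "the bottles will be classified into codes A and B", and each letter stands for one whole group. An independent investigator receives the medication, passes on the coded bottles and holds the key: "At the end of the intervention, the independent investigator will be asked to reveal the coding of the medications". I read this as the end of the trial's intervention.
- **Dispensing.** Under Stages of the study and data collection: "A closed bottle containing 100 tablets (treatment A or B) will be provided according to the random assignment". During follow-up, "the reminder will be reviewed twice a week and the remaining tablets will be counted in the bottles". Neither sentence says who does this.
- **The look.** The text between Flowchart 1 and Ethical Considerations gives a total of 106 and says that, unless adverse reactions lead to suspension, "recruitment will continue until a sample size of 53 subjects is met and at this point the intermediate analysis will be performed". It refers to Flowchart 2, which is not in the readable text.
- **The SAP.** Besides descriptive statistics it lists "Independent t-test and Chi-square test for the difference between the two study groups" and an ANOVA over the five time periods. It does not mention an interim analysis.
- **The graders.** Under Standardization: "The master's student and a social service student will be standardized, the evaluation will be in pairs and independently". On the WHO scale, the Instruments section says: "This instrument was designed based on objective signs (erythema or ulcer) and subjective signs (mucosal sensitivity, ability to swallow".

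**The concern.** With only two codes, the blind fails for all children together. If anyone recognises one child's tablet as zinc, every child with that letter is known to be on zinc. A table of mucositis by letter has much the same effect for a reader who expects zinc to work.

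The planned look could produce such a table. A comparison of groups at that point has to be made by letter or by opening the code before its stated time. No readable section says who runs the look, who sees the result, or that the two graders are kept from it. The Confidentiality section gives the study's researchers access to the databases and does not exclude the graders.

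What is at stake is the grading of the remaining 53 or so children. Incidence turns on grade 0 versus grade I, which rests on pain and erythema. A grader with a belief about the letters could shift that boundary without intending to, and blinding lost midway cannot be restored.

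**Working it through.** **1. The plan's own figures** (Sample size calculation): [1.96·√(2·0.75·0.25) + 0.84·√(0.75·0.25 + 2·0.47·0.53)]² / 0.28² = 45.84, rounded up to 46. Then 46 × 1.15 = 52.9, so 53 per group and 106 in total. Half of 106 is 53, so the look appears to be at 53 of 106. Because 53 is also the per-group size, the plan should confirm this.

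**2. Split at the look.** Blocks of 6, run as one sequence: 53 = 8 × 6 + 5. That is 24 per letter plus a 2/3 split of the last five, or 26 and 27.

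**3. How much a by-letter table reveals.** Let X ~ Bin(n₁, p₁) be placebo cases and Y ~ Bin(n₂, p₂) zinc cases. The exact probability that the zinc letter shows strictly lower incidence is the sum of P(X=x)·P(Y=y) over all pairs with y/n₂ < x/n₁.

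| Children per letter | 75% vs 47% | 75% vs 60% |
|---|---|---|
| 26 placebo, 27 zinc | 0.983 | 0.870 |
| 16 and 16 | 0.932 | 0.768 |
| 13 and 13 | 0.905 | 0.733 |

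The 75% vs 60% column is my assumption of a smaller effect. The 13-16 rows count only children who have finished treatment, assuming even accrual of 106 over the 10 months from August 2019 to May 2020 (10.6 per month). With 2 to 2.5 months of treatment, 53 − 2 × 10.6 = 31.8 and 53 − 2.5 × 10.6 = 26.5 have finished; halved, about 16 and 13. The truth probably lies between the rows, because the Background puts onset at 3 to 10 days, so many children still on treatment already have an outcome.

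**4. What drift would do if zinc has no effect** (illustration only). Incidence is 75% in both groups, with 26/27 children at the look and 27/26 after it. After the look, graded incidence moves d/2 down in the letter that looked better and d/2 up in the other. The final test is an uncorrected chi-square at 53 per group, two-sided 0.05, with 2,000,000 simulated trials. The sizes of d are my assumption; the documents give none.

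| Drift d | After any gap | Only after a gap ≥ 15 points |
|---|---|---|
| 0 | 5.3% | 5.3% |
| 5 points | 9.8% | about 7.7% |
| 10 points | 17.1% | about 10.6% |

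A gap of at least 15 points arises in about 20% of trials with no effect. In the any-gap column, about half of the errors favour zinc: 4.9% and 8.5%, against 2.6% with no drift. If the table held only 14 children per letter, the any-gap figures would be 8.9% and 14.6%.

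**5. The two calculations answer different questions.** Step 3 assumes that zinc works. Step 4 assumes that it does not, and then the better-looking letter is zinc only about half the time. The 98% must not be multiplied into, or read alongside, the false-positive rates as one scenario.

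**The case against.** - **The look may not compare groups.** Its paragraph opens with reducing risk and suspending for adverse reactions, so a safety-only or pooled look is a natural reading. The one hint the other way is a garbled sentence under Benefits that puts the absence of a difference favouring the intervention next to suspension; it does not name the look. This stands, and the point is conditional on it.
- **Flowchart 2 could settle who sees what.** This also stands. A reader might infer that the trial has no stopping rule, boundary or firewall. The documents do not support that, because the page that may hold them is not shown.
- **Graders may never see a letter.** Dispensing and tablet counts are described in the passive, and the data sheet under Information collection method lists no treatment letter. Knowledge of each child's letter is therefore an inference from a small team. A reader might take the three people under Financing as the whole team. That is a resource list; the Methodology also has an independent code-holder, a separate randomiser and a mucositis expert.
- **Drift is assumed.** Standardisation to a weighted kappa of at least 0.61 gives some protection, and with no drift there is no inflation.

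None of this removes the two-letter code, which is fragile even without a look, or the SAP's silence.

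**Conclusion.** The point holds as a weakness in coding and in the description of the look. It does not show that the blind will be broken. Three things are firm: one letter per group, a planned analysis at 53 subjects missing from the SAP, and no readable text that keeps a by-letter result from the graders. If groups are compared and zinc works as planned, such a table would largely reveal the code (about 98%, or 91-93% with 13-16 per letter; 73-87% if the true difference is 15 points).

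Bias in the final result needs three further steps: the table reaches the graders, they know each child's letter, and their grading drifts. A reader might take 17.1% as the trial's expected false-positive rate. It is the upper end of an illustration in which drift of 10 points follows every gap, however small, and only about half of those errors favour zinc. A reader might also think that numbered bottles alone solve the matter. They do not if results by group are shared together with each child's assignment, so the restriction on who sees the result is needed as well.

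Minor to moderate; a cheap improvement.

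**What to change.** 1. For bottles not yet dispensed, replace A and B with individual numbers from the randomisation list, and put that number in the sealed envelope. Keep group letters off bottles, data sheets and the working database. The existing independent investigator holds the list. A resupply bottle carries the child's same number.
2. Any by-group interim result is seen only by someone who does not grade mucositis. The study team is told only to continue or stop.
3. Describe the look in the SAP consistently with Flowchart 2: what is analysed, who runs it, who sees it, and whether 53 is the total.

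**Cost.** New labels, a numbered list and one person outside grading, with no change to sample size. Second bottles must be matched: with 30-day months, two tablets daily for 2 to 2.5 months is 120-150 tablets against 100 per bottle, while one tablet daily is 60-75. Those second bottles are needed under A/B labels too. If 25-50% of the 106 take two tablets (assumption), about 27-53 bottles need matching.

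The protocol is dated October 2019 but inclusion runs from August 2019. At 10.6 per month over about three months, roughly 30 children could already hold A/B bottles. They keep them; for those children the shared letter remains and item 2 is the protection.
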